5.8.1 Cerebral Edema

Due to the immunologic nature of pembrolizumab administration, cerebral edema could theoretically result as a consequence of pembrolizumab administration due to immune infiltration of the brain. Symptoms related to cerebral edema may include headache or neurologic deficits that are either new or worsened. Patients with any signs or symptoms of cerebral edema should be treated as clinically appropriate including initiation or increased systemic corticosteroid dosing, initiation of bevacizumab administered per local institutional practice, treatment with an osmotic diuretic or surgical decompression. An investigator may initiate bevacizumab per local institutional practice if significant mass effect is seen on an MRI in anticipation of subsequent clinical decline. Subsequent pembrolizumab dosing should be immediately interrupted if significant clinical symptoms attributable to cerebral edema develop. Treatment with additional pembrolizumab doses may only be re-initiated if clinically significant symptoms attributable to cerebral edema have resolved to grade ≤ 1 or pre-treatment baseline. Patients who develop CTCAE 5.0 grade 4 cerebral edema attributable to pembrolizumab administration should not receive further pembrolizumab doses and should discontinue study therapy.

NOTE: every effort should be made to not exceed a corticosteroid dose of > 4 mg / day between date of registration and on-study surgery. If a corticosteroid of > 4 mg / day is necessary a participant following registration and prior to on-study surgery, the treating investigator should reach out to the Overall PI to confirm the participant's evaluability for tumor tissue studies.

5.8.2 Diet/Activity/Other Considerations

5.8.2.1 Diet

Subjects should maintain a normal diet unless modifications are required to manage an AE such as diarrhea, nausea or vomiting.

5.8.2.2 Contraception

Pembrolizumab may have adverse effects on a fetus in utero. Furthermore, it is not known if pembrolizumab has transient adverse effects on the composition of sperm. Non-pregnant, non-breast-feeding women may be enrolled if they are willing to use 2 methods of birth control or are considered highly unlikely to conceive. Highly unlikely to conceive is defined as 1) surgically sterilized, or 2) postmenopausal (a woman who is ≥ 45 years of age and has not had menses for greater than 1 year will be considered postmenopausal), or 3) not heterosexually active for the duration of the study. The two birth control methods can be either two barrier methods or a barrier method plus a hormonal method to prevent pregnancy. Subjects should start using birth control from study Visit 1 throughout the study period up to 120 days after the last dose of study therapy.

The following are considered adequate barrier methods of contraception: diaphragm, condom (by the partner), copper intrauterine device, sponge, or spermicide. Appropriate hormonal contraceptives will include any registered and marketed contraceptive agent that contains an

estrogen and/or a progestational agent (including oral, subcutaneous, intrauterine, or intramuscular agents).

Subjects should be informed that taking the study medication may involve unknown risks to the fetus (unborn baby) if pregnancy were to occur during the study. In order to participate in the study they must adhere to the contraception requirement (described above) for the duration of the study and during the follow-up period defined in section 6.2 Reporting of Pregnancy and Lactation to the Sponsor and to Merck. If there is any question that a subject will not reliably comply with the requirements for contraception, that subject should not be entered into the study.

5.8.2.3 Use in Pregnancy

If a subject inadvertently becomes pregnant while on treatment with pembrolizumab, the subject will immediately be removed from the study. The site will contact the subject at least monthly and document the subject's status until the pregnancy has been completed or terminated. The outcome of the pregnancy will be reported to the Sponsor and to Merck without delay and within 1 working day if the outcome is a serious adverse experience (e.g., death, abortion, congenital anomaly, or other disabling or life-threatening complication to the mother or newborn).

The study investigator will make every effort to obtain permission to follow the outcome of the pregnancy and report the condition of the fetus or newborn to the Sponsor. If a male subject impregnates his female partner the study personnel at the site must be informed immediately and the pregnancy reported to the Sponsor and to Merck and followed as described above and in Section 6.2.

5.8.2.4 Use in Nursing Women

It is unknown whether pembrolizumab is excreted in human milk. Since many drugs are excreted in human milk, and because of the potential for serious adverse reactions in the nursing infant, subjects who are breast-feeding are not eligible for enrollment.

5.9 Duration of Therapy and Criteria for Removal from Study Treatment

Duration of therapy will depend on individual response, evidence of disease progression and tolerance. Treatment may continue until one of the following criteria applies:

- The subject or legal representative (such as a parent or legal guardian) withdraws consent.
- Confirmed radiographic disease progression

Note: For unconfirmed radiographic disease progression, please see Section 10.5

Note: A subject may be granted an exception to continue on treatment with confirmed radiographic progression if clinically stable or clinically improved, please see Section 10.5.

- Unacceptable adverse experiences
- Intercurrent illness that prevents further administration of treatment
- Investigator's decision to withdraw the subject
- The subject has a confirmed positive serum pregnancy test

- Noncompliance with trial treatment or procedure requirements
- General or specific changes in the participant's condition render the participant unacceptable for further treatment in the judgment of the treating investigator
- Administrative reasons

Participants will be removed from the protocol therapy when any of these criteria apply. The reason for removal from protocol therapy, and the date the participant was removed, must be documented in the case report form (CRF). Alternative care options will be discussed with the participant.

When a participant is removed from protocol therapy and/or is off of the study, the relevant Off-Treatment/Off-Study information will be updated in OnCore.

In the event of unusual or life-threatening complications, treating investigators must immediately notify the Overall PI, [name].

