1. OBJECTIVES

1.1 Study Design

This is a multicenter, randomized, open-label, pilot surgical trial of pembrolizumab (MK-3475) among bevacizumab naive, surgically resectable recurrent glioblastoma patients. Please see Figure 1 for Schema.

Group A: pembrolizumab (MK-3475) at 200 mg IV within 14 ± 5 days prior to surgery. Post-surgery subjects will receive pembrolizumab at 200mg IV every three weeks.

Group B: no pembrolizumab (MK-3475) prior to surgery. Post-surgery subjects will receive pembrolizumab at 200mg IV every three weeks.

After recovering from surgery, subjects will be evaluated every 6 weeks with radiographic imaging to assess response to treatment. The Response Assessment in Neuro-Oncology (RANO) criteria will be used as the efficacy endpoint of response rate. A modified RANO (iRANO)¹¹¹ (as described in Section 10.0) will be used to evaluate response and progression in an exploratory fashion due to the tumor response patterns seen with pembrolizumab treatment (e.g., tumor flare). Adverse events will be monitored throughout the trial and graded in severity according to the guidelines outlined in the NCI Common Terminology Criteria for Adverse Events (CTCAE) version 5.0. Treatment with study therapy will continue until documented disease progression, unacceptable adverse event(s), intercurrent illness that prevents further administration of treatment, investigator's decision to withdraw the subject, subject withdraws consent, pregnancy of the subject, noncompliance with trial treatment or procedure requirements, or administrative reasons. After the end of treatment, each subject will be followed for 30 days for adverse event monitoring and 90 days for serious adverse event reporting. Subjects who discontinue treatment for reasons other than disease progression will have post-treatment follow-up of disease status until disease progression, initiation of a non-study cancer treatment, withdrawing consent, or becoming lost to follow -up. All subjects will be followed by telephone contact or medical record review for overall survival until death, withdrawal of consent or the end of the study, whichever comes first.

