be closely monitored with MRIs every cycle (approximately every 6 weeks) during this period. Patients who have radiographic evidence of further progression after up to three months, or who decline significantly at anytime, will be classified as progressive with the date of disease progression back-dated to the first date that the subject met criteria for progression and such subjects will be discontinued from study therapy. Although the kinetics of pseudoprogression due to immune checkpoint blockade among glioblastoma patients is currently unknown, three months is a reasonable estimate based on: 1) the peak time for XRT/daily temozolomide-related pseudoprogression is usually within three months of completion for glioblastoma patients^{107,108} and; 2) three months is also the most common timeframe for pseudoprogression observed among patients with advanced melanoma or other solid tumors treated with PD-1/PD-L1 immune checkpoint blockade to date.^{66,69,109}

Among patients on this study with initial radiographic PD, tumor assessment should be repeated regularly (every cycle, approximately every 6 weeks) in order to confirm PD with the option of continuing treatment as described below while awaiting radiologic confirmation of progression. If repeat imaging shows a stabilization or reduction in the tumor burden compared to the initial scan demonstrating PD, treatment may be continued / resumed. If repeat imaging after up to three months confirms progressive disease, then the date of disease progression will be the first date the subject met criteria for progression and subjects will be discontinued from study therapy. Subjects who have confirmed disease progression will discontinue study medication and enter the follow up/survival phase of the study. In determining whether or not the tumor burden has increased or decreased, investigators should consider all target lesions as well as non-target lesions.

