- Tumor Enhancement to Define Progression: RANO expanded the previously utilized Macdonald criteria¹⁰⁶ to include the development of “significantly” increased T2 or FLAIR abnormality in the definition of progressive disease because such changes can be a major component defining radiographic progression following therapeutic use of VEGF/VEGFR-targeting therapeutics which are known to elicit potent anti-permeability changes that limit contrast uptake. However, immune based therapies are expected to be associated with inflammatory changes that may include edema. Therefore, radiographic progressive disease will be defined by assessment of enhancing tumor and will not declare tumor progression based on the presence of T2 or FLAIR changes alone as outlined in RANO because:
 - There is no expectation that immunotherapy agents including PD-1 inhibitors will falsely diminish enhancing tumor burden as has been noted with anti-angiogenic therapies; and
 - Immune based therapies are expected to induce inflammatory responses which may be associated with increased edema and T2/FLAIR changes. Such radiographic finding may inaccurately be interpreted to represent tumor progression (i.e. pseudoprogression).

In subjects who have initial evidence of radiographic PD, it is at the discretion of the treating physician whether to continue a subject on study treatment for up to three months pending

confirmation of PD on follow-up imaging. This clinical judgment decision should be based on the subject's overall clinical condition, including performance status, clinical symptoms, and laboratory data. Subjects may receive study treatment while waiting for confirmation of PD if they are not experiencing significant clinical decline and the subject is adequately tolerating study therapy (if a subject is required to discontinue study treatment for toxicity as defined per protocol section 5, then they must be taken off-treatment).

When feasible, study therapy should not be discontinued until radiographic progression is confirmed. This allowance to continue treatment despite initial radiologic progression takes into account the observation that some subjects can have a transient tumor flare in the first few months after the start of immunotherapy, but with subsequent disease response.¹⁰⁵ Subjects that are exhibiting significant neurologic decline are not required to have repeat imaging for confirmation of progressive disease.

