Table 8 Imaging and Treatment After 1st Radiologic Evidence of PD

	No Significant Neurologic Decline		Significant Neurologic Decline	
	Imaging	Treatment	Imaging	Treatment
1 st radiologic evidence of PD	Repeat imaging (every cycle, approximately every 6 weeks) for up to 3 months to confirm PD	May continue study treatment at the Investigator's discretion for up to 3 months while awaiting confirmatory scans	Repeat imaging >6 weeks later to confirm PD if possible	Discontinue treatment
Repeat scan up to 3 months after 1 st radiologic evidence confirms PD	No additional imaging required; date of tumor progression back-dated to date of initial radiographic PD	Discontinue treatment	No additional imaging required	Not applicable
Repeat scan shows SD, PR or CR	Continue regularly scheduled imaging assessments every 6 weeks	Continue study treatment at the Investigator's discretion	Continue regularly scheduled imaging assessments every 6 weeks	May restart study treatment if condition has improved and/or clinically stable per Investigator's discretion

Participants with progressive radiographic findings are encouraged to undergo surgical intervention in order to delineate pseudoprogression due to inflammation associated with PD-1 blockade from true tumor progression. Participants with histopathologic findings of significant immune infiltrate and evolving gliosis will be allowed to continue study therapy. In contrast, those with clear evidence of progressive tumor by histopathologic evaluation will be defined as progressive and discontinued from study therapy. For such patients, the date of tumor progression will be the first date the participant met radiographic criteria for PD

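### Section 5.9 lets clinically stable patients stay on treatment after confirmed radiographic progression and cites Section 10.5, but Section 10.5 and Table 8 take those patients off treatment

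*Combined protocol and SAP*

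**What the plan says.** Section 5.9 lists the reasons for ending study treatment, one of which is confirmed radiographic disease progression. The list closes with: "Participants will be removed from the protocol therapy when any of these criteria apply". Two notes sit under the progression item. The first deals with unconfirmed progression and refers to Section 10.5. The second reads "A subject may be granted an exception to continue on treatment with confirmed radiographic progression if clinically stable or clinically improved" and also refers to Section 10.5.

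Section 10.5 deals with continuing beyond initial progression. While a confirmatory scan is pending it is permissive: "Subjects may receive study treatment while waiting for confirmation of PD if they are not experiencing significant clinical decline", for up to three months. Once progression is confirmed it is not: "Subjects who have confirmed disease progression will discontinue study medication and enter the follow up/survival phase of the study". It also says that when repeat imaging confirms progression, the progression date is the first date the "subject met criteria for progression and subjects will be discontinued from study therapy". In the confirmed-progression row of Table 8, for patients without significant neurologic decline, the imaging entry is "No additional imaging required; date of tumor progression back-dated to date of initial radiographic PD" and the treatment entry is to discontinue.

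Section 1.1 says: "Treatment with study therapy will continue until documented disease progression". The Synopsis requires that the progression be both documented and confirmed. The group descriptions in Section 5 refer only to tumor progression. None of these three places mentions an exception.

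**The concern.** Section 5.9 relies on Section 10.5 for the terms of an exception, and Section 10.5 rules that exception out. Sites then have no single stopping rule, and monitors have no single standard for judging compliance. Appendix B, Section 3.9.1, classes a departure from the protocol without prospective IRB approval as a violation, so a site using the Section 5.9 exception could be both compliant and in violation.

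The statistical stake is that time on treatment depends on which section a site follows. Safety is a primary objective in both stages (Section 1.2.3). Adverse event follow-up runs for 30 days after the end of treatment, and serious event reporting for 90 days (Section 5.10). Section 12.2.9 summarises exposure as the number of cycles in which the subject is infused. Section 12.2.6.3 compares second PFS and OS between Groups A and B by log-rank test, and treatment after progression can bear on both. The trial is open-label (Section 5.4), and nothing says who grants an exception, on what criteria, or how it is recorded. Uneven use between groups is possible and could not readily be examined afterwards.

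**Working it through.** The plan gives no figure to reproduce on this point. The check is a comparison of the sections, followed by tracing which endpoints the difference can reach.

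**1. One patient, two instructions.** Take a patient whose repeat scan confirms progression and who is clinically stable.

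| Source | Instruction for this patient |
|---|---|
| Section 5.9, list item | Remove from treatment |
| Section 5.9, second note | May continue by exception; see Section 10.5 |
| Section 10.5, text | Discontinue and enter follow-up; no exception |
| Table 8, confirmed progression, no significant neurologic decline | Discontinue |
| Synopsis | Treat until documented and confirmed progression; no exception |
| Section 1.1 | Treat until documented progression; confirmation not mentioned |
| Section 5, group descriptions | Treat until tumor progression; confirmation not mentioned |

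The Table 8 row covers the clinically stable patients whom the Section 5.9 note would exempt.

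**2. Does Section 10.5 supply the exception elsewhere?** It allows treatment after radiographic progression in three situations.

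- *Awaiting confirmation, up to three months.* Progression is not yet confirmed. The first note in Section 5.9 already covers this, so the second note must mean something else.
- *Repeat scan shows SD, PR or CR.* The Table 8 entry "May restart study treatment if condition has improved and/or clinically stable per Investigator's discretion" resembles the Section 5.9 condition, but it sits in the row where progression has not been confirmed.
- *Surgery shows immune infiltrate and gliosis.* The condition is a tissue finding, not clinical stability or improvement.

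None of these is an exception for confirmed radiographic progression on the ground of clinical status.

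**3. Which endpoints can be affected?**

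- *TIL density and the cell cycle signature:* measured on tissue from the protocol surgery, before any post-surgical dose. Not affected.
- *PFS6:* depends on the first progression date, which precedes the decision to continue after confirmation. Section 10.5 back-dates confirmed progression to that date. PFS6 is also analysed with the groups pooled (Section 12.1). Not affected.
- *Exposure and safety follow-up:* affected for each exception. A cycle is 42 days with infusions on Days 1 and 22 (Section 5.1). A patient who continues for k further full cycles adds k to the exposure count and receives 2k more infusions. The last dose, and with it the 30-day and 90-day windows, moves later by 42k days. One extra cycle means 2 infusions and 42 days; two mean 4 infusions and 84 days.
- *Second PFS and OS:* follow the first progression and so can be affected. Both are exploratory (Section 1.4).

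The number of exceptions and the value of k are not in the documents, so a trial-level effect cannot be calculated. Stage 2 recruits to Group A only, so any change over time in how the exception is used would fall mainly on that group.

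**The case against.** The strongest reply is that Section 5.9 states a default and a discretionary exception. The default is to stop at confirmed progression, which agrees with Section 10.5, and an exception to a default is not an opposing rule. On this reading the fault is only a cross-reference to a section that omits the terms. That describes Section 5.9 fairly when it is read alone. It does not dispose of the problem, because Section 10.5 and Table 8 are unconditional for the same patients, and Section 5.9 names Section 10.5 as its authority.

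Several other points stand:

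- Section 10.5 does allow some treatment after radiographic progression, although on different conditions.
- The Section 1.1 discrepancy is the weaker part. It is a design overview, and documented progression is less specific than confirmed progression rather than opposed to it. The Synopsis agrees with Sections 5.9 and 10.5 on confirmation.
- The safety windows are tied to the end of treatment and move with it. Longer treatment extends adverse event capture and loses none of it.
- The case report form already records the date and reason for removal, and treatment forms record each dose, so duration of exposure will be known. What is missing is a required record that an exception was granted and why.
- Section 12.2.6 treats efficacy p-values as nominal.
- Uneven granting of exceptions between groups is a possibility, not something the documents show.

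**Conclusion.** The concern holds. For a clinically stable patient with confirmed radiographic progression, Section 5.9 permits continuation, while Section 10.5 and Table 8 require discontinuation. The citation in Section 5.9 does not resolve this. The inconsistency over confirmation in Section 1.1 and the Section 5 group descriptions is real but secondary.

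The consequence is limited. The tissue primary endpoints and PFS6 are untouched. Exposure, the timing of safety follow-up, and the exploratory second PFS and OS comparisons can vary with the section a site follows. The trial-level size cannot be derived from the documents. The conclusion rests on reading the second note in Section 5.9 as written, that is, as applying to confirmed progression, and on no assumed number of exceptions. The sections should be reconciled, but the primary biomarker analyses do not depend on it.

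**What to change.** Reconcile the Synopsis, Sections 1.1, 5, 5.9 and 10.5, and Table 8 so that all state one stopping rule and use the word *confirmed* consistently. Either the exception goes into Section 10.5 and Table 8 with its conditions and the person who approves it, or the note in Section 5.9 comes out. That choice is clinical and belongs to the sponsor.

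If exceptions remain possible, or have already been granted, add a case report form item for each one giving the date, the reason, the approver, and the number of doses after confirmed progression. Report the count and the added exposure by group and stage alongside the Section 12.2.9 summary. Say how second PFS and OS will be described for these patients.

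The cost is a protocol wording amendment, plus one short form item if exceptions stay. Sample size and the planned tests do not change.
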